## 8.5 Criteria for Premature Permanent Discontinuation of Study Product

See Section 6.6 for guidance regarding participant management in the event of early termination or withdrawal from study participation. Administration of study product will be permanently discontinued in the following circumstances:

- Participant intention to discontinue study product or study follow-up
- During the oral lead-in phase, sustained non-adherence to oral regimen that, in the opinion of the investigator and in consultation with the CMC, warrants early study product discontinuation.
- Sustained non-adherence to injection visit schedule that, in the opinion of the investigator and in consultation with the CMC, warrants early study product discontinuation (per IoR discretion, a temporary product hold may be initially implemented; see Section 8.5).
- The participant requires treatment with prohibited medications (see Section 5.7).
- During the oral lead-in phase, confirmed pregnancy; see Section 8.4 for product management during injectable phase in the context of a positive pregnancy test.

- Participants of childbearing potential who are engaging in sexual activity that could lead to
  pregnancy refuse use of an effective contraceptive method without an intention to
  resume/initiate.
- The participant experiences an adverse event that requires discontinuation as defined in Section 8.1.
- Virologic failure as described in Section 8.3.
- The site investigator determines that further administration of study product would be detrimental to the participant's health or well-being.
- New data become available that indicate study products should be discontinued as determined by the CMC.

Participants who permanently discontinue study product should resume (non-study provided) cART as follows:

- Cohort 1 and Cohort 2a participants during the oral lead-in phase: as soon as possible and within 4 weeks of their last oral study product use.
- All participants during injectable phase and on a Q4W dosing regimen: within 4 weeks of their last study product injection.
- All participants during injectable phase and on a Q8W dosing regimen: at 8 weeks ( $\pm 7$  days) after their last study product injections.

Participants who permanently discontinue oral study product will be instructed to return all oral study products to the site clinic as soon as possible.

See Section 6.6 for the specified participants who will be followed per the LSFU visit schedule upon permanent discontinuation of study product.

Participants who prematurely permanently discontinue study product during the oral lead-in phase for reasons other than pregnancy or are otherwise not eligible to progress to the injection phase will be terminated from the study. These participants should complete an Early Termination visit 28 days after last oral study product use; see Section 8.6 below for additional guidance in the event of termination from the study.

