# 6.6 Long-Term Safety and Washout PK Follow-Up (LSFU) Visits

Participants who prematurely and permanently discontinue injectable study product, or participants who discontinue study product use (either oral or injectable study product) due to pregnancy, will be followed for an additional 48 weeks to assess long-term safety and washout PK of the study products. Additionally, participants who receive their injections at their final scheduled follow-up visit (Week 72 for Cohort 1, Week 48 for Cohort 2a, and Week 44 for Cohort 2b) but do not wish to continue the CAB LA + RPV LA regimen outside of the study will resume (non-study provided) ART and enter into the LSFU visit schedule. Participants will resume (non-study provided) oral cART as soon as possible, and within 4 weeks, or 8 weeks (±7 days), of discontinuing study product depending on the study product dosing regimen which was discontinued (i.e., O4W or O8W dosing regimen). The LSFU visits will be scheduled approximately 4, 8, 24, 36, and 48 weeks after the last injection, after which participants will exit the study. Participants who permanently discontinue study product (either oral or injectable study product) due to pregnancy will be followed for 48 weeks, based on the date of the positive confirmatory pregnancy test result. For participants who become pregnant during LSFU visits, the LSFU visits will continue as scheduled and not restart. All LSFU visit procedures will be conducted, with the exception that pregnancy testing will not be required for participants who are currently pregnant. See Section 8.2 for further details on management of pregnant participants and pregnancy outcome.

During LSFU, a single random PK sample will be collected at each visit as shown in the procedural tables below.

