## **Appendix II: Target Visit Dates and Visit Windows**

		ugh Week 72) and COHORT 2A				
Study Visit Name	Target Visit Date	Target Visit Window	Min/Max requirements (from previous IM)			
Week 2	14 days from entry	-7/+6 days from target date	N/A			
Week 4a	28 days from entry	-7/+10 days from the target date	N/A			
Week 4b	As soon as lab results are and no later than 42 days	available from the Week 4a visit from entry	N/A			
Week 5	3 days from Week 4b	-1 day/+4 days from the target	N/A			
Week 6	12 days from Week 4b	date	N/A			
Week 8	28 days from Week 4b	-7 days/+3 days from the target date	minimum of 3 weeks (21 days) and a maximum of 4 weeks and 3 days (31 days) apart, as counted from the previous injection			
Week 9	3 days from Week 8	-1 day/+5 days from the target date	N/A			
Week 12	56 days from Week 4b					
Week 16	84 days from Week 4b	-7 days/+3 days from the target date				
Week 20	112 days from Week 4b	_				
Week 24	140 days from Week 4b					
Week 28	168 days from Week 4b	_				
Week 32	196 days from Week 4b	_				
Week 36	224 days from Week 4b					
Week 40	252 days from Week 4b		minimum of 3 weeks (21 days) and a			
Week 44	280 days from Week 4b		maximum of 5 weeks (35 days) apart, as counted from the previous injection			
Week 48	308 days from Week 4b	-7/+7 days from the target date				
Week 52	336 days from Week 4b					
Week 56	364 days from Week 4b					
Week 60	392 days from Week 4b					
Week 64	420 days from Week 4b					
Week 68	448 days from Week 4b					
Week 72	476 days from Week 4b					

Q8W: COHORT 1 (through Week 72) and COHORT 2A (through Week 48 only)								
Study Visit Name	Target Visit Date	Target Visit Window	Min/Max requirements (from previous IM)					
Week 2	14 days from entry	-7/+6 days from target date	N/A					
Week 4a	28 days from entry	-7/+10 days from target date	N/A					
Week 4b	As soon as lab results are and no later than 42 days	available from the Week 4a visit from entry	N/A					
Week 5	3 days from Week 4b	-1 day/+4 days from the target	N/A					
Week 6	12 days from Week 4b	date	N/A					
Week 8	28 days from Week 4b	-7 days/+3 days from the target date	a minimum of 3 weeks (21 days) and a maximum of 4 weeks and 3 days (31 days) from the Week 4b injection					
Week 9	3 days from Week 8	-1 day/+5 days from the target date	N/A					
Week 12	56 days from Week 4b		N/A					

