Week 16	84 days from Week 4b	-7 days/+3 days from the target date	a minimum of 7 weeks (49 days) and a maximum of 8 weeks and 3 days (59 days) from the Week 8 injection					
Week 20	112 days from Week 4b		N/A					
Week 24	140 days from Week 4b		a minimum of 7 weeks (49 days) and a maximum of 9 weeks (63 days) from the previous regularly scheduled injection					
Week 28	168 days from Week 4b		N/A					
Week 32	196 days from Week 4b		a minimum of 7 weeks (49 days) and a maximum of 9 weeks (63 days) from the previous regularly scheduled injection					
Week 36	224 days from Week 4b		N/A					
Week 40	252 days from Week 4b		a minimum of 7 weeks (49 days) and a maximum of 9 weeks (63 days) from the previous regularly scheduled injection					
Week 44	280 days from Week 4b	-7 days/+7 days from the target	N/A					
Week 48	308 days from Week 4b	date	a minimum of 7 weeks (49 days) and a maximum of 9 weeks (63 days) from the previous regularly scheduled injection					
Week 52	336 days from Week 4b		N/A					
Week 56	364 days from Week 4b		a minimum of 7 weeks (49 days) and a maximum of 9 weeks (63 days) from the previous regularly scheduled injection					
Week 60	392 days from Week 4b		N/A					
Week 64	420 days from Week 4b		a minimum of 7 weeks (49 days) and a maximum of 9 weeks (63 days) from the previous regularly scheduled injection					
Week 68	448 days from Week 4b		N/A					

		a minimum of 7 weeks (49 days) and a
Week 72	476 days from Week 4b	maximum of 9 weeks (63 days) from the
		previous regularly scheduled injection

Q4W: COHORT 2b					
Study Visit Name	Target Visit Date	Target Visit Window	Min/Max requirements (from previous IM)		
Day 3	3 days from entry	-1/+4 days from target date	N/A		
Week 2	14 days from entry	-7/+6 days from the target date	N/A		
Week 4	28 days from entry	-7/+3 days from the target date	A minimum of 3 weeks (21 days) and a maximum of 4 weeks and 3 days (31 days) from the previous injection.		
Week 8	56 days from entry		A minimum of 3 weeks (21 days) and a maximum of 5 weeks (35 days) apart, as counted from the previous injection		
Week 12	84 days from entry				
Week 16	112 days from entry				
Week 20	140 days from entry	-7/ + 7 days from the target date			
Week 24	168 days from entry				
Week 28	196 days from entry				
Week 32	224 days from entry				
Week 36	252 days from entry				
Week 40	280 days from entry				
Week 44	308 days from entry				

Q8W: COHORT 2b				

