Study Visit Name	Target Visit Date	Target Visit Window	Min/Max requirements (from previous IM)	
Day 3	3 days from entry	-1/+4 days from target date	N/A	
Week 2	14 days from entry	-7/+6 days from the target date	N/A	
Week 4	28 days from entry	-7/+3 days from the target date	A minimum of 3 weeks (21 days) and a maximum of 4 weeks and 3 days (31 days) from the previous injection	
Week 8	56 days from entry		N/A	
Week 12	84 days from entry		A minimum of 7 weeks (49 days) and a maximum of 8 weeks and 3 days (59 days) from the previous injection.	
Week 16	112 days from entry		N/A	
Week 20	140 days from entry		A minimum of 7 weeks (49 days) and a maximum of 9 weeks (63 days) from the previous regularly scheduled injection.	
Week 24	168 days from entry		N/A	
Week 28	196 days from entry		A minimum of 7 weeks (49 days) and a maximum of 9 weeks (63 days) from the previous regularly scheduled injection.  N/A	
Week 32	224 days from entry	-7/ + 7 days from the target date		
Week 36	252 days from entry		A minimum of 7 weeks (49 days) and a maximum of 9 weeks (63 days) from the previous regularly scheduled injection.	
Week 40	280 days from entry		N/A	
Week 44	308 days from entry		A minimum of 7 weeks (49 days) and a maximum of 9 weeks (63 days) from the previous regularly scheduled injection.	

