# **Injectable Dosing:**

**Table III: Injection Interval** 

III.A	Q. 4 weeks
III.B	Doses 1 and 2, 4 weeks apart, then Q. 8 weeks

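### The Section 8.5 restart time for background cART on Q8W (day 49–63 after the last injections) does not fit the first Q8W interval, where the next injection is due at day 28

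*Protocol*

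**What the plan says.** Protocol Section 8.5 introduces the rule with "Participants who permanently discontinue study product should resume (non-study provided) cART as follows" and then gives one line per situation. For Q4W in the injectable phase, restart is within 4 weeks of the last injection. For Q8W the line is "All participants during injectable phase and on a Q8W dosing regimen: at 8 weeks" (±7 days) after the last injections. It covers every Q8W participant in the injectable phase and makes no exception for a child who has had one injection only.

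Section 6.6, to which Section 8.5 sends the reader, has participants resume "oral cART as soon as possible, and within 4 weeks, or 8 weeks (±7 days), of discontinuing study product", with the 4- or 8-week limit chosen by the regimen that was stopped.

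The Q8W regimen does not start with an 8-week gap. Table III of Appendix VII defines it as "Doses 1 and 2, 4 weeks apart, then Q. 8 weeks". Appendix II sets the second Q8W injection at a target of 28 days after the first, with limits of "a minimum of 3 weeks (21 days) and a maximum of 4 weeks and 3 days (31 days) from the Week 4b injection" in Cohorts 1 and 2a and "A minimum of 3 weeks (21 days) and a maximum of 4 weeks and 3 days (31 days) from the previous injection" in Cohort 2b.

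Confirmed virologic failure has its own rule in Section 8.3: restart as soon as possible and within 4 weeks, whatever the regimen.

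**The concern.** The restart time appears to be built on the 8-week dosing interval. In the first interval the next dose is due after 4 weeks, so the rule sends a child who stops after one injection back to cART well after the date on which the protocol would have given more drug.

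Elsewhere the protocol ties antiretroviral cover to the due date. The Q4W line in Section 8.5 restarts cART by the time the next injection would fall due. Section 5.1.3 asks for oral bridging to begin ideally on the target date, or within the window, of the missed injection. So a Q8W child bridging a missed second injection is covered from about day 28, while the same child stopping for good is given day 49–63.

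What is at stake is participant management. Section 1.2.5.1 names sub-therapeutic concentrations as a possible route to virologic failure and resistance, and names a resistance risk after injections are stopped. Early stopping needs no adverse event: the Section 8.5 list includes "Participant intention to discontinue study product or study follow-up", and names no CMC step for that route.

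**Working it through.** Only day counts are needed.

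**Inputs**
- Section 8.5, Q8W restart: 8 weeks ±7 days after the last injections.
- Section 8.5, Q4W restart: within 4 weeks of the last injection.
- Appendix II, Q8W, injection 1 to injection 2: target day 28, allowed day 21–31 (Week 4b to Week 8 in Cohorts 1 and 2a; Entry to Week 4 in Cohort 2b).
- Appendix II, Q8W, Week 24 onward in Cohorts 1 and 2a, and Week 20 onward in Cohort 2b: allowed 49–63 days from the previous injection.
- Appendix II, Q4W, injection 1 to injection 2: target day 28, allowed day 21–31.

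**Step 1. The plan's window.** 8 × 7 = 56; 56 − 7 = 49 and 56 + 7 = 63. Restart falls on day 49–63 after the last injections.

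**Step 2. Later Q8W intervals.** The allowed injection window is day 49–63. It is the same as the restart window, so there is no mismatch.

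**Step 3. First Q8W interval.**
- Against the due date: 49 − 28 = 21 and 63 − 28 = 35, so 21–35 days after the second injection was due.
- Against the last allowed day: 49 − 31 = 18 and 63 − 31 = 32, so 18–32 days after it.

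**Step 4. The Q4W child in the same position.** The first interval is identical (day 28, allowed 21–31), and Section 8.5 has this child restart by 4 × 7 = day 28. With the next dose due on the same day, restart for the Q8W child is 49 − 28 = 21 to 63 − 28 = 35 days later than the Q4W limit.

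**Step 5. Sections 8.5 and 6.6 side by side.** Section 8.5 fixes a time *at* which to restart. Section 6.6 sets a limit *within* which to restart and adds that it should be as soon as possible. Counted from the last injection, both have the same outer limit, day 63. They differ on whether earlier restart is intended. Neither refers to the day-28 due date.

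**The case against.** Several points on the other side stand.

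- Section 8.5 says *should*, and Section 6.6 asks for restart as soon as possible, so nothing forbids a site from acting sooner.
- A child who stops injections enters LSFU, where the first visit is targeted 28 days after the last injection, the day the second injection would have been due. It includes HIV-1 RNA, a PK sample and adherence counseling. This is a partial safeguard: the window of −14/+28 days runs from day 14 to day 56, and the visit does not change the restart rule.
- The CMC must be consulted on missed injection visits (Section 6.1.1) and temporary holds (Section 8.4), which will catch many early stops.
- Q8W comes into use only after an SMC review (Section 9.5.4), and the MOP and memorandum that would carry implementation detail are not shown.

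A reader might also infer two stronger claims.

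- **Two different clocks.** Section 6.6 counts from discontinuing study product, which could be taken as a later decision date. The documents do not support building on that. Section 6.6 ties its limit to the dosing interval, which makes sense only from the last injection; the same section counts LSFU visits from the last injection; and Section 8.5 states that clock outright. The wording could be clearer, but no separate, later deadline is established.
- **A shown period of inadequate drug exposure.** The protocol gives no concentrations at day 49–63 after a single injection, Q8W doses are still to be chosen from Appendix VII, and nothing states that a first injection covers only 4 weeks. A mismatch with the dosing calendar is not by itself a coverage gap.

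**Conclusion.** The rule as written is wrong for one defined group: children who start injections on Q8W and permanently stop after the first one, for a reason other than confirmed virologic failure. For them Section 8.5 places cART restart 21–35 days after the second injection was due, and no exception appears anywhere in the protocol. Section 6.6 softens this but conflicts with Section 8.5 in its limit word and still allows about 8 weeks.

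Severity is minor. The size of the group is not given and is probably small, Q8W is conditional, and a day-28 visit is planned. No effect on sample size, analysis or any study estimate is claimed. The conclusion rests on Section 8.5 and Appendix II as printed and on counting from the last injection; unseen operational documents might already deal with it.

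**What to change.** Use the same sentence in Sections 8.5 and 6.6, counted explicitly from the last injection. Q8W participants who permanently stop resume cART as soon as possible, and no later than:

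- 4 weeks (by day 31, the last allowed day for the second injection) if only the first injection was received;
- 8 weeks (+7 days) otherwise.

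If the stop first becomes known after that date, cART resumes immediately. Keep the separate 4-week rule for confirmed virologic failure in Section 8.3.

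The cost is one line in each of two sections. It adds no visits, samples or data items. It would best be in place before any child starts injections on Q8W.

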# 8.6 Participant Withdrawal or Termination from the Study

Participants may voluntarily withdraw from the study at any time, and the site investigator may also, at their discretion, discontinue the participant from the study at any time under the following circumstances:

- Participant re-locates away from the study site (with no options to transfer to another site) or is otherwise determined to be lost-to-follow-up
- Investigator or designee determines that continued participation in the study would be unsafe or otherwise not in the best interest of the participant, after consultation with the CMC
- The study is stopped or canceled by the sponsors or government or regulatory authorities
- Site participation in the study is canceled by the sponsors, government or regulatory authorities, the sIRB (for US sites), or site IRBs/ECs (for non-US sites)

In each of the circumstances listed above, except the study being stopped or cancelled, the CMC should be consulted before terminating the participant from follow-up. Participants who are withdrawn from the study will not be replaced.

Should the permitting parent or legal guardian of an enrolled participant die or no longer be available for any reason, study product should be temporarily held and no further study products should be

administered and no further study-specific evaluations should be performed until written parental permission for continued study participation is obtained from an authorized guardian, as defined locally. Study sites may continue to provide care for the participant as needed and as appropriate (outside of the study), consistent with the local standard of care, but no study-specific procedures may be performed. If an authorized guardian cannot be identified, or if the authorized guardian does not permit continued study participation, the participant must be terminated from the study. Refer to Section 8.4 for additional guidance on communication with the CMC for temporary study product holds, and Section 13 for legal guardian permission for study participation.

For any participant who withdraws/is withdrawn or is terminated from the study prior to scheduled completion of follow-up, study staff will document the reason for the withdrawal or termination in detail and will make every effort to complete final evaluations as described in Section 6.6. In the event that the circumstances that led to a participant's withdrawal or termination change (e.g., he or she returns to the study site area after having re-located previously), the site investigator or designee should contact the CMC to discuss options for resumption of follow-up.

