## 8.4 Deferring Study Product and Criteria for Temporary Hold of Study Product

At each study product administration time point, the site investigator or designee must confirm participant eligibility to receive study product (see Section 6.8). Study product administration must be deferred consistent with the guidance provided in Section 8.4.

For any other significant medical condition that, in the opinion of the investigator, would make it unsafe to administer study product or make it difficult to assess for subsequent study drug related adverse events, if present on the scheduled day of study product administration, administration must be deferred, and the CMC should be consulted on next steps and continued study product management.

For all temporary holds, both study products should be held, and the CMC should be consulted as soon as possible and within 48 hours; the CMC may recommend resuming a (non-study provided) cART regimen in these situations. For participants resuming a cART regimen for the duration of a temporary study product hold, site staff should provide the participant and the participant's parent or guardian with referrals to non-study sources of treatment for the participant, as applicable. See the IMPAACT 2036 MOP for operational consideration and guidance.

Study product will be temporarily held from a participant for any of the following reasons:

- Study product management per Sections 8.1 through 8.4.
- Report of use of prohibited concomitant medications (See Section 5.7). Study product use may
  resume upon consultation with the CMC and when the participant reports that he/she is no
  longer taking the prohibited medication, provided other reasons for temporary study product
  hold/permanent discontinuation do not apply. The CMC should be consulted in all cases of a
  participant reporting taking a prohibited concomitant medication during the course of the study.
- The participant is unable or unwilling to comply with required study procedures, such as protocol-required laboratory assessments or injectable study product visits, or otherwise might be put at undue risk to their safety and well-being by continuing study product use, according to the judgment of the site investigator. The site investigator must consult the CMC on all temporary study product holds instituted for this reason, for further guidance on resuming study product use, continuing the temporary hold, or progressing to permanent discontinuation.

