## 13.2 Vulnerable Participants

NIH policy requires that children be included in clinical research conducted or supported by the NIH when appropriate (23). This study complies with that policy and will provide clinical research data to inform study product dosing for children. Nonetheless, the children who take part in this study are considered vulnerable participants per 45 CFR 46 Subpart D.

IRBs/ECs must determine the level of risk to children in the categories specified in 45 CFR 46.404-407. Documentation of this determination is required to complete the DAIDS protocol registration process described in Section 14.2, and the risk category assigned by the IRB/EC further determines the parental permission requirements for the study at each site. Per 45 CFR 46.408 (b), the IRB/EC may find that the permission of one parent is sufficient for research to be conducted under 46.404 or 46.405. If the IRB/EC finds that the research is covered by 46.406 or 46.407, both parents must give their permission, unless one parent is deceased, unknown, incompetent, or not reasonably available or when only one parent has legal responsibility for the care and custody of the child (as determined

locally). IRBs/ECs must document their risk determination. Parental permission will be documented on site-specific parental permission forms, and study sites should adapt the signature pages of their site-specific forms as needed to accommodate the parental permission requirements associated with the IRB/EC determination.

Study sites must comply with requirements for enrolling minors in clinical research as specified in the DAIDS SCORE Manual. In addition, to the US regulations cited above, sites must also comply with all applicable local and national and international guidelines and regulations. When multiple different sets of requirements apply, the most stringent requirements must be followed.

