### 13.3.1 Parental Permission and Informed Assent for Child Study Participants

Written parental permission for study participation will be obtained from each participant's parent or legal guardian before any study-specific procedures are performed. It is generally expected that the permission of one parent (or legal guardian) will be sufficient for child participation in this study. However, parental permission requirements at each site will depend on the IRB/EC risk determination as described in Section 13.3; all applicable IRB/EC requirements must be followed. If applicable per local regulations, the potential participant is considered a minor who is legally able to provide informed consent, written informed consent for study participation will be obtained from the potential participant instead of parental or legal guardian permission before any study-specific procedures are performed.

Permission for the child's participation will include a description of what is currently known about the safety and efficacy of the study products and the context of current local standards of care for HIV-1 care and treatment. Should the participant be unaware of their HIV-1 status, the parental permission process may be conducted with the parent or legal guardian separately and without the presence of the participant, per IRB/EC policies.

When applicable per site IRB/EC policies and procedures, written assent will also be obtained from each child before any study-specific procedures are performed. If the participant does not provide assent, or the parent or legal guardian does not provide permission, the participant will not be enrolled in the study. Minor participants who assent to a study and later withdraw that assent will not be maintained in the study against their will, even if their parent or legal guardian still wants and permits them to participate.

Should the permitting parent or legal guardian of an enrolled participant die or no longer be available for any reason, all applicable IRB/EC policies and procedures should be followed. If the participant is doing well on study drug, it is generally expected that they will stay on study drug with safety monitoring evaluations performed consistent with the local standard of care. Other study-specific evaluations (outside the standard of care) should not be performed until written permission for continued study participation is obtained from the child's new legal guardian. If a new legal guardian

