cannot be identified, or if the new legal guardian does not permit continued study participation, the child must be withdrawn from the study.

The assent process will include an age-appropriate discussion of study participation. Sites should follow IRB/EC policies when determining whether the assent process should be conducted with both the parent or legal guardian and the participant present. Non-US sites may develop multiple assent forms, if desired, in anticipation of different information needs across the study age range. When preparing site-specific assent forms, sites may remove or modify the wording included in the sample assent forms in order to provide the most appropriate information and level of detail, consistent with applicable IRB/EC policies and procedures. Given the study age range, it is expected that some potential participants will be aware of their HIV status whereas others will not. To avoid unintentional disclosure of HIV status, the sample assent forms provided in Appendix V do not refer to HIV status or treatment of HIV. For potential participants who are aware of their status, study staff may provide more specific and HIV-related information when discussing the assent form.

For participants who do not meet IRB/EC criteria for providing assent or consent at the time of screening and enrollment, if such criteria are met during follow-up, assent or consent should be obtained when the criteria are met.

As part of the parental permission and informed assent processes, parents or legal guardians will be asked whether they agree to storage and future research testing of biological specimens remaining after all protocol-specified testing has been completed. This storage and future research testing is optional and may be declined with no impact on other aspects of study participation.

In accordance with the requirements for enrolling minors in clinical research as specified in the DAIDS SCORE Manual, all sites must establish and maintain written procedures describing the standards that will be followed to identify who may serve as legal guardian for an enrolled child, reflective of applicable IRB/EC guidance for conduct of human subjects research within the context of available local law, regulation, or government policy.

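### When the permitting guardian dies or becomes unavailable, Section 8.6 holds study product but Section 13.3.1 generally expects a child doing well to stay on it, and no text expressly ranks the two

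*Protocol*

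**What the plan says.** Both sections open with the same triggering clause about loss of the permitting parent or guardian.

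- **Protocol 8.6** says that "study product should be temporarily held and no further study products should be" administered, and that study-specific evaluations also stop, until an authorized guardian gives written permission. It states no exception for a child who is doing well. Care outside the study may continue. The paragraph's closing cross-reference, which begins by naming Section 8.4, promises the reader "additional guidance on communication with the CMC for temporary study product holds, and Section 13 for legal guardian permission for study participation".
- **Protocol 13.3.1** says first that "all applicable IRB/EC policies and procedures should be followed". It then says that, if the child is doing well on study drug, "it is generally expected that they will stay on study drug", with safety monitoring in line with the local standard of care. Only the other study-specific evaluations wait for the new guardian's permission.

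The two sections end in the same place. If no guardian is found, or "if the new legal guardian does not permit continued study participation, the child must be withdrawn from the study"; Section 8.6 likewise ends in termination from the study. They differ only on study product while permission is outstanding.

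**The concern.** A site that reads Section 8.6 stops both drugs, and a site that reads Section 13.3.1 may keep dosing. Each can point to protocol text, so children in the same position may be treated differently.

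Each reading has a cost for the child. Under Section 13.3.1 a child aged two to under 12 could receive a depot injection, which Section 1.3.1 notes cannot be removed, while the written permission that Section 8.6 asks for is outstanding. Under Section 8.6 a child in oral lead-in, who gave up pre-study cART at entry (Section 5.1), is at once without study drug, and a child on injections may miss a dose. Oral bridging (Section 5.1.3) does not fill that gap because it is itself study product.

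**Working it through.** The protocol states no figure on this point. The check sets the texts side by side and looks for anything that ranks them.

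| Question | Section 8.6 | Section 13.3.1 |
|---|---|---|
| Trigger | Loss of permitting guardian | Same |
| First instruction | Hold product | Follow IRB/EC policy |
| Product while permission is pending | Held, no stated exception | Generally continued if doing well |
| Evaluations while permission is pending | No study-specific evaluations | Standard-of-care safety monitoring only |
| No guardian, or refusal | Leaves the study | Leaves the study |

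**Candidate tie-breakers**

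1. *IRB/EC deferral (13.3.1).* A site whose committee requires a hold can hold without breaching Section 13.3.1. A site that doses on the general expectation still departs from Section 8.6. Local policies can differ, so the deferral permits divergence.
2. *Section 13.2: "When multiple different sets of requirements apply, the most stringent requirements must be followed".* This leans towards the hold. It closes a paragraph on regulations and guidelines for enrolling minors, and does not speak to two sections of one protocol.
3. *Cross-references in 8.6.* Sending the reader to Section 8.4 for holds suggests that Section 8 governs product. The other reference is to Section 13, where the opposite expectation sits.
4. *Section 8.4 list, first item: "Study product management per Sections 8.1 through 8.4".* Section 8.6 lies outside that range, and loss of the guardian is not named elsewhere in the list.
5. *Section 8.4 list, third item.* This requires a hold, with CMC consultation, when the participant cannot comply with required procedures such as laboratory assessments or injection visits. A child whose study-specific evaluations are suspended arguably fits, but that is an inference; the item does not mention missing permission.
6. *Section 6.9.* Before any dispensing or injection, the scheduled clinical evaluations must be done, the previous visit's laboratory results reviewed and, where applicable, a negative pregnancy test obtained. If local care does not supply these, dosing under Section 13.3.1 cannot proceed. The laboratory item concerns the previous visit, however, so results drawn before the guardian was lost could still satisfy it for one further injection.

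Items 2, 3, 5 and 6 point to the hold. None says so expressly.

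**cART timing, if it is to be stated.** Inputs are the Section 8.5 restart times and the Appendix II maximum gaps since the previous injection.

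- Q4W: the 8.5 limit is 4 × 7 = 28 days. Maximum gaps are 31 days (second injection) and 35 days (later injections). 31 − 28 = 3 and 35 − 28 = 7, so the 8.5 limit comes first.
- Q8W after the first injection only: the 8.5 time is 56 ± 7, that is day 49 to 63. The second injection is due by day 31. 49 − 31 = 18 and 63 − 31 = 32, so the injection date comes first by 18 to 32 days.
- Q8W later: maximum gaps of 59 and 63 days lie within day 49 to 63.

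Neither date is always the earlier, so a safe rule takes whichever comes first.

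**The case against.** The best case for leaving the text alone is that the protocol already resolves the matter in practice. Section 13.3.1 is only a general expectation placed after a deferral to IRB/EC policy. Sections 6.9 and 8.4 constrain dosing while study evaluations are suspended. Section 8.4 also covers the hold itself: for all temporary holds "the CMC should be consulted as soon as possible and within 48 hours", and the CMC may recommend non-study cART. Much of this stands. It limits the harm on both sides and keeps the point minor. It does not make the two product instructions agree.

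It can also be said that choosing the hold is a judgement, since continuity of treatment protects a suppressed child. That is fair: either single instruction would remove the contradiction. The hold is the better choice because Sections 8.6, 8.4 and 6.9 already lean that way and a depot dose cannot be withdrawn.

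Three stronger readings are tempting, and the documents do not support them:

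- A reader might infer that Section 13.3.1 authorizes injections without valid permission. Whether the original permission survives depends on local law and IRB/EC policy, which the protocol does not give, and Section 6.9 restricts dosing in any case.
- A reader might infer that the Section 8.5 cART times should simply be applied to this hold. They are written for permanent discontinuation, and for a Q8W child after one injection they fall 18 to 32 days after the second injection is due.
- A reader might infer damage to the analysis. Any child who received a dose stays in the All Treated set, and no stated sample size, endpoint or evaluability rule changes.

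**Conclusion.** The inconsistency is real: one event, two opposite defaults on study product, and no express ranking. The surrounding text favours the hold but leaves it to inference. There is no statistical effect. The frequency of the event is not given and is not estimated here. This is a minor participant-protection and consistency correction. It rests on reading both sections as current and equally binding, which their wording supports, and on no assumption about local law.

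**What to change.** In Section 13.3.1, replace the sentence expecting the child to stay on study drug with the Section 8.6 hold pending written permission. Add a cross-reference to Sections 8.6 and 8.4, so that the CMC is consulted within 48 hours and non-study cART follows its recommendation. The IRB/EC sentence can remain for how a new guardian is identified and permission obtained, but it should not read as a second instruction on product.

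No cART timing need be added. If it is, cART should start no later than the earlier of the next due injection and the Section 8.5 limit. In oral lead-in, where dosing is daily, that means as soon as possible.

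The cost is protocol wording only. No analysis, sample size or evaluability rule changes.
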